9.3.1 Sensitivity Analysis of the Primary and Secondary Endpoints

The primary and secondary endpoint analyses will be repeated for the RF and MMIA analysis sets as noted those respective sections.

Additionally, the analysis of ORS at Weeks 12, 24, 36, and 52, and the number and percentage of subjects with 12- and 24-week confirmed improvement for the EDSS+ and each of its components will be repeated based on multiple imputation (MI). First, a full dataset will be imputed using full data imputation MCMC. Data will be imputed for the EDSS, T25FW, 9HPT-D and 9HPT-ND in a continuous fashion for each endpoint separately. Then, the definition of clinically significant improvement/no change/clinically significant worsening as seen in Section 4.3.1 will be applied to determine the components of the ORS or 12- or 24- week confirmed improvement status. The imputation model will include treatment group, type of MS, baseline use of immunomodulator therapies, baseline variable for the respective endpoint being imputed, and the non-missing post-baseline values for the variable that will be imputed (value at Week 12, 24, 36, 52, 64 and 76). The number of imputed datasets will be 30, and the random seed will be 123455. The ORS at each visit noted above will be summarized for each treatment group and compared to placebo using ANCOVA, with baseline values for each component of the EDSS + included in the model. The responder status with 12- and 24-week confirmed improvement will be analyzed with a logistic regression as noted in Section 9.4.1.

M14-397 – Statistical Analysis Plan Version 2.0 – 06 Jan 2021

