4.3 Endpoint

4.3.1 Primary Efficacy Endpoint

The primary efficacy endpoint is the Overall Response Score (ORS) at Week 52.

ORS is a composite score derived from 4 components:

- Expanded Disability Status Scale (EDSS)
- Timed 25-Foot Walk (T25FW)
- 9-Hole Peg Test in the dominant hand (9HPT-D)
- 9HPT in the non-dominant hand (9HPT-ND)

The EDSS + is a composite derived from the EDSS, T25FW, 9HPT-D and 9HPT-ND where responder status is defined as a clinical meaningful improvement on one or more of these endpoints. Hereafter, the EDSS, T25FW, 9HPT-D and 9HPT-ND will also be referred to as "components of the EDSS +" or "components of the ORS."

The ORS is scored with a range from -4 to +4 at each assessment for all post-baseline visits. Scores for each component are assessed relative to their baseline value: -1 if there is clinically significant worsening, 0 if the change does not meet the clinically significant threshold criteria, or +1 if there is clinically significant improvement. The scores for all components are summed at each assessment. If any of the 4 components of the ORS are missing within a visit window, then the ORS will be considered missing for that visit.

The clinically significant change thresholds for EDSS, T25FW and 9HPT are provided in the following table.

	Score of ORS Components at Post-Baseline Visits			
ORS Components	-1 (Clinically Significant Worsening)	0 (No Clinically Significant Change)	l (Clinically Significant Improvement)	
EDSS change from baseline	\geq 1 if baseline EDSS \leq 5.5; \geq 0.5 if baseline EDSS \geq 6.0	-0.5, 0 or 0.5 if baseline EDSS $\leq 5.5;$ 0 if baseline EDSS ≥ 6.0	≤ -1 if baseline EDSS ≤ 5.5 ; ≤ -0.5 if baseline EDSS ≥ 6.0	
T25FW change from baseline	≥20%	> -20% and < 20%	\leq -20%	
9HPT-D change from baseline	\geq 20%	> -20% and < 20%	\leq -20%	
9HPT-ND change from baseline	≥20%	> -20% and < 20%	\leq -20%	

4.3.2 **Secondary Efficacy Endpoints**

The secondary efficacy endpoints include:

- Disability improvement responder status (Yes or No) on the EDSS+
- ORS at Weeks 12, 24, and 36

Exploratory Efficacy Endpoints 4.3.3

The exploratory efficacy endpoints include:

- Disability improvement response rate on the EDSS, T25FW, 9HPT-D, and 9HPT-ND at Weeks 12, 24, 36, and 52, and the EDSS + at Weeks 12, 24, and 36.
- Change from Baseline on the T25FW, 9HPT-D, 9HPT-ND at Weeks 12, 24, 36, and 52

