9.2 Primary Efficacy Analysis

The primary efficacy variable is the ORS at Week 52 and secondary efficacy variables are the ORS at Weeks 12, 24, and 36. The ORS will be summarized continuously as observed (including n, mean, standard deviation, minimum, median and maximum) at each visit.

The frequency and percentage of subjects with each ORS score in the range of -4 to +4 will also be provided by treatment group at each visit. The data will be analyzed and summarized as observed, i.e., no imputations will be implemented.

The comparisons between the each elezanumab group and placebo for the primary efficacy endpoint ORS at each scheduled visit during the study will be performed using an MMRM. The ORS for each treatment group at scheduled visits and overall will be estimated from the model. The within group LS mean 95% confidence interval, pooled standard deviation, effect size, and 95% confidence interval for the effect size will also be presented by treatment group. The model will include the fixed effects of treatment, visit, diagnosis of MS (PPMS or nrSPMS), and background MS immunotherapy (Yes or No), and the treatment-by-visit interaction with baseline scores (EDSS, T25FW, 9HPT-D, 9HPT-ND) as covariates. The REPEATED statement will be used for visit with blocks in the covariance matrix identified by subject nested within treatment group. The unstructured covariance structure will be used to estimate the within subject variance-covariance. If the model fails to converge, the first order autoregressive (AR[1]) covariance structure will be substituted. If the model still fails to converge, the compound

symmetry (CS) covariance structure will be substituted. Denominator degrees of freedom will be computed using the Kenward-Roger method.

This will be repeated for the RF and MMIA sets.

The posterior probability that each elezanumab group's effect size is greater than 0.1, 0.3, and 0.5 will be presented for the mITT analysis set.

The ORS and corresponding 95% confidence interval based on the MMRM for the mITT analysis set will be plotted at each time point during the treatment period by treatment group.

The post-treatment ORS scores will be summarized continuously as observed.

9.3 **Secondary Efficacy Analyses**

Disability improvement on the EDSS + indicates clinically significant improvement on at least 1 of the components of the EDSS + (EDSS, T25FW, 9HPT [either hand]) as defined by the clinically significant change thresholds in Section 4.3.1).

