Improvement responder status on the EDSS + and each of its components will be analyzed by time point based on the criteria in Section 4.3.1. No confirmation will be required, i.e., improvement at the analysis time point only is required to be considered a responder.

The analysis will be presented at each time point with the number and percentage of responders, and the 95% confidence interval for the proportion of subjects based on Wald confidence limits, and the odds ratio and corresponding 95% confidence interval based on the logistic regression model including baseline as a covariate and treatment as a main effect. The model for the EDSS + will include the baseline EDSS, baseline T25FW, baseline 9HPT-D, baseline 9HPT-ND as covariates and treatment as a main effect. This will be presented based on the mITT, RF and MMIA analysis sets using non-responder

imputation. The logistic regression analysis will be repeated for the mITT analysis set based on the same multiple imputation as detailed in Section 9.3.1.

A summary of the improvement responder status on the EDSS + and each of its components will be presented for the mITT analysis set as observed.

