The analyses for confirmed disability improvement will be repeated for the RF and MMIA analysis sets as noted those respective sections.

9.4.2 **Disability Progression**

Disability progression on the EDSS + indicates clinically significant worsening on at least 1 of the components of the EDSS + (EDSS, T25FW, 9HPT [either hand]) as defined by the clinically significant change thresholds in Section 4.3.1). This will be based on the imputed dataset described in Section 9.3.1.

Progression on the EDSS + and each of its components will be analyzed by time point based on the criteria in Section 4.3.1. No confirmation will be required, i.e., progression at the analysis time point only is required.

The analysis will be presented at each time point with the number and percentage of subjects, and the 95% confidence interval for the proportion of subjects based on Wald

confidence limits, and the odds ratio and corresponding 95% confidence interval based on the logistic regression model including baseline as a covariate and treatment as a main effect.

9.4.3 **T25FW**

The change from baseline in the T25FW during the Treatment Period will be analyzed using an MMRM. In addition to the summaries noted in Section 9.1, the pooled standard deviation, effect size, and 95% confidence interval of the effect size will be noted.

9.4.4 9HPT

The change from baseline in the 9HPT-D and 9HPT-ND during the Treatment Period will be analyzed using an MMRM. In addition to the summaries noted in Section 9.1, the pooled standard deviation, effect size, and 95% confidence interval of the effect size will be noted.

9.4.5 **Exploratory Patient and Clinician Measured Scales**

The change from baseline in the total score for the MSIS-29, the total score for the BAC -Tower of London, the total score for the BAC - Verbal Memory, BAC - Tower of London T-score, BAC - Verbal Memory T-score, and the overall symptom score and most bothersome symptom score for the MSIOA will be analyzed at the collected time points using an MMRM.

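### Imputing the four ORS components separately modestly overstates any-of-four EDSS+ rates at imputed visits and narrows the imputed ORS, if component changes are positively correlated

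*SAP*

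**What the plan says.** SAP 9.3.1 describes the imputation in three parts.

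- Unit of imputation: "Data will be imputed for the EDSS, T25FW, 9HPT-D and 9HPT-ND in a continuous fashion for each endpoint separately".
- Predictors: "The imputation model will include treatment group, type of MS, baseline use of immunomodulator therapies", then "baseline variable for the respective endpoint being imputed, and the non-missing post-baseline values for the variable that will be imputed". No sentence brings a second component into any of the four models.
- Size: "The number of imputed datasets will be 30".

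The imputed values are then cut at the SAP 4.3.1 thresholds and combined. ORS adds four scores of −1, 0 or +1. EDSS+ is an any-of-four rule: 4.3.1 describes a composite "where responder status is defined as a clinical meaningful improvement on one or more of these endpoints", and 9.3 repeats that "Disability improvement on the EDSS + indicates clinically significant improvement on at least 1 of the components of the EDSS" is needed.

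Four results draw on the imputed set:

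- the ORS sensitivity analysis by ANCOVA (9.3.1);
- confirmed EDSS+ improvement, as a repeat analysis (9.3.1);
- the repeat logistic regression for EDSS+ improvement, "based on the same multiple imputation as detailed in Section 9.3.1" (9.3);
- disability progression in 9.4.2: "This will be based on the imputed dataset described in Section 9.3.1".

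The main analyses do not use it. ORS is analysed by MMRM without imputation (4.7, 9.2). EDSS+ improvement and confirmed improvement use non-responder imputation (9.3, 9.4.1).

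**The concern.** A sum and an any-of-four rule both depend on how the components move together within a subject. Four separate models do not carry that dependence beyond what each component's own history holds. If the true correlation is positive, the imputed components are too nearly independent. The chance that at least one improves, or at least one worsens, is then too high, and the spread of the sum is too small.

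Partial visits raise a related problem. SAP 8.5 plans to tabulate them, and 4.3.1 sets ORS to missing when any component is missing, so the MMRM loses that visit's ORS. The imputation could recover it, but it ignores the components seen at the same visit.

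At stake are the level of the reported EDSS+ rates, above all progression, and the credibility of the ORS missing-data check. A sensitivity analysis with too little imputation variance looks more reassuring than it should.

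**Working it through.** **Inputs from the documents.** Four components and their scoring (SAP 4.3.1); the imputation models (9.3.1); about 90 subjects, 30 per arm, about 10% dropout (4.4).

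**Assumed inputs.** Correlation ρ between component changes of 0.3 and 0.5, with 0 as reference; 10% improving and 20% worsening per component; correlation 0.6 between visits within a component; 10 to 20% of Week 52 values imputed.

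**1. The plan's own figure.** The plan gives no figure for the imputation. Its one planning figure is about 80% power for an effect size of 0.59 at one-sided 0.1. With 30 × 0.9 = 27 per arm, the noncentrality is 0.59 × √(27/2) = 2.17 and power is 80.8%. It reproduces and does not depend on this point.

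**2. Limiting case: no post-baseline history.** Separate imputation makes the components independent.
- Any improved: 1 − 0.9⁴ = 34.4%.
- Any worsened: 1 − 0.8⁴ = 59.0%.
- ORS SD: √[4 × (0.1 + 0.2 − 0.1²)] = √1.16 = 1.08.
- Mean ORS: 4 × (0.1 − 0.2) = −0.40, whatever the correlation.

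**3. Correlation kept through own history.** With Weeks 12, 24 and 36 seen, a component's own history explains 3 × 0.6² / (1 + 2 × 0.6) = 0.49 of its Week 52 variance. Separately imputed values keep about ρ × 0.49: 0.15 instead of 0.3, and 0.25 instead of 0.5 (simulated 0.14 and 0.24).

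**4. Large simulation, subjects with Week 52 imputed (joint / separate).**

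| Visits seen | ρ | Any improved, % | Any worsened, % | ORS SD |
|---|---|---|---|---|
| 12–36 | 0 | 34.4 / 34.3 | 59.1 / 59.1 | 1.08 / 1.08 |
| 12–36 | 0.3 | 29.5 / 32.2 | 50.3 / 54.6 | 1.38 / 1.24 |
| 12–36 | 0.5 | 25.9 / 30.5 | 44.5 / 51.9 | 1.55 / 1.33 |
| 12–36, 64, 76 | 0.3 | 29.6 / 31.9 | 50.2 / 54.2 | 1.38 / 1.25 |
| 12–36, 64, 76 | 0.5 | 25.8 / 30.2 | 44.4 / 51.3 | 1.55 / 1.35 |
| 12 only | 0.5 | 25.8 / 31.5 | 44.5 / 53.8 | 1.55 / 1.27 |
| None | 0.5 | 25.8 / 34.4 | 44.6 / 59.0 | 1.55 / 1.08 |

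Joint imputation recovers the full-data values in every row, and mean ORS stays at about −0.40. With Weeks 12 to 36 seen, the excess is 2.3 to 4.6 points for improvement and 4.0 to 7.4 for worsening, and the SD is about 10 to 15% low. With less history the gap is wider.

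**5. Second simulation: 90 subjects, half-point EDSS, log times, 20% missing, other component rates.** Separate minus joint at ρ = 0.3 / 0.5:
- improvement: 47 − 44 = 3 and 45 − 40 = 5 points;
- progression: 58 − 54 = 4 and 56 − 51 = 5 points;
- between-imputation variance of the ORS contrast: 22% / 34% lower.

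Joint imputation itself lay 2 to 4 points above full data here (44 v 42, 40 v 37, 54 v 52, 51 v 47). Only the gap between separate and joint can be charged to separate imputation.

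**6. Whole arm.** Bias is the imputed fraction times the excess.
- Improvement: 0.10 × 2.7 = 0.3 up to 0.20 × 4.6 = 0.9 points.
- Worsening: 0.10 × 4.3 = 0.4 up to 0.20 × 7.4 = 1.5 points.

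Simulation with 90 subjects put the range at about 0.3 to 1.3. A 40-replicate check at ρ = 0.5 and 20% missing gave 26.1 − 25.7 = 0.4 and 45.9 − 44.3 = 1.6. One subject in an arm of 30 is 3.3 points.

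**7. Contrasts.** In simulation at 10 to 20% missing, the active-minus-placebo difference in EDSS+ progression under separate imputation was within 0.5 points of full data, and chained equations were no closer (for example −8.4 full data, −8.0 separate, −7.8 chained). The standard error of the ORS contrast was 3 to 6% smaller than under chained equations.

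**8. Partial visit, one component missing.** Adding the other three at that visit cuts the missing one's unexplained variance by 3ρ² / (1 + 2ρ): 17% at 0.3 and 38% at 0.5. Separate imputation overstates improvement by 1.2 / 2.2 points and worsening by 2.1 / 3.5 points at such visits.

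**The case against.** The strongest reply is that little of consequence rests on this imputation. That largely stands. For ORS and EDSS+ improvement it is a supplementary check, and EDSS+ progression is an exploratory endpoint in a Phase 2a study with no multiplicity adjustment. The whole-arm shift is smaller than one subject per arm. Nor do the documents give component correlations, component rates or a missing fraction; the nearest figure is the 10% planned dropout. Confidence is therefore high for the direction, given positive correlation, and not for the size.

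Four stronger readings are tempting, and the documents do not support them.

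- A reader might infer that the primary result is biased. It is not: the MMRM uses no imputed values, and mean ORS is unchanged even in the imputed set.
- A reader might infer that 9.3.1 is the only source of information on worsening. SAP 9.6 plots component worsening as observed at Weeks 12 to 52, and single-component rates are not biased by separate imputation. Only the any-of-four progression rate rests on the imputed set alone.
- A reader might take a between-imputation variance a quarter to a third too small to mean a standard error understated to that degree. That variance is a small part of the total, and the effect on the standard error was 3 to 6%.
- A reader might suppose that the imputed components are wholly unrelated. About half of the correlation survives when three earlier visits are seen.

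What remains is that the models omit dependence that the endpoints need, and that the omission is cheap to repair. Positive correlation is plausible, since two components are the same test in each hand and all four measure disability.

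**Conclusion.** The point holds as a low-severity improvement. With component correlations of 0.3 to 0.5 and most earlier visits seen, separate imputation overstates EDSS+ rates among imputed visits, relative to joint imputation, by about 2 to 5 points (improvement) and 4 to 7 points (progression). The imputed ORS SD is about 10 to 15% too low, and the between-imputation variance of the ORS contrast is roughly a quarter to a third too small. At 10 to 20% imputed, the rate excess over a whole arm is about 0.3 to 1.3 points, with single checks reaching 1.6. It acts alike in all arms, so the documents give no ground for reading this as a distortion of the treatment effect. EDSS+ progression in 9.4.2 is the most exposed result; the imputation-based ORS and EDSS+ improvement analyses are affected to a lesser degree. All sizes rest on the stated assumptions and vanish at zero correlation.

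**What to change.** Change three pieces of SAP 9.3.1 together: the instruction to impute the endpoints separately, the MCMC wording, and the predictor list that admits only a component's own values. Changing the first alone would leave the section contradicting itself.

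Replace them with one joint or chained-equations (FCS) imputation of all four components. Each component at a visit is predicted by treatment, the two strata, its own baseline and other visits, and the other three components at that visit. Chained equations are the more workable form: a full multivariate model would carry 4 × 7 = 28 outcome variables (baseline and six visits each) in about 90 subjects.

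Score ORS, EDSS+ improvement, confirmed improvement and progression (9.3, 9.3.1, 9.4.1, 9.4.2) from that single imputed set. Add an as-observed EDSS+ progression summary to 9.4.2, to match the one that 9.3 already gives for improvement. If the analysis has already been run, rerun the imputation, or state the limitation beside the progression results and the ORS sensitivity analysis.

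The cost is SAP wording, some reprogramming and about three more predictors per model. No new data are needed.

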9.4 Other Efficacy Analyses

Change from baseline treatment comparison at each visit will be conducted using an MMRM model including treatment group, visit, treatment-by-visit interaction, and stratification factors as fixed effects, the baseline values associated with the endpoint as covariates. The REPEATED statement will be used for visit with blocks in the covariance matrix identified by subject nested within treatment group. The unstructured covariance structure will be used to estimate the within subject variance-covariance. If the model fails to converge, the first order autoregressive (AR[1]) covariance structure will be substituted. If the model still fails to converge, the compound symmetry (CS) covariance structure will be substituted. Denominator degrees of freedom will be computed using the Kenward-Roger method.

For binary efficacy endpoints, the frequency and percentage will be provided by treatment group unless otherwise noted.

9.4.1 Confirmed Improvement on the EDSS + and its components

Confirmed 12-week disability improvement on the EDSS + or components of the EDSS + indicates a subject has clinically significant improvement at a visit as well as the next visit for one or more EDSS + components, or if the next visit is missing, the subsequent visit. Confirmation may include assessments collected in the post-treatment follow-up period. The improvement confirmation must be in the same component of the EDSS +. If a subject has improvement in more than one component of the EDSS +, the subject must have confirmation in at least one of the same components to be considered as having confirmed disability improvement. For example, if a subject has clinically significant improvement in the T25FW at Week 12, the subject must have clinically significant improvement in the same component of the EDSS + at Week 24 (or if Week 24 is missing, Week 36) to be considered to have confirmed improvement.

Confirmed 24-week improvement on the EDSS + or components of the EDSS + indicates a subject has clinically significant improvement at 3 consecutive visits, or if one of the two subsequent visits are missing, subject demonstrates clinically significant

improvement at two of the subsequent three visits. Improvement status after confirmed improvement is not considered, i.e., if a subject has disability improvement in one component of the EDSS + at Week 12 and Week 24, then this subject is considered to have 12-week confirmed disability improvement regardless of a Week 36 status of clinically significant worsening, no clinically significant change, or clinically significant improvement.

The 12-week and 24-week confirmed disability improvement response rate will be summarized for the study for the EDSS +, as well as each of the individual components for the mITT, RF, and MMIA analysis sets based on a non-responder imputation. The frequency and percentage will be provided by treatment group. The treatment comparison will be conducted using the logistic regression model adjusted for the stratification factors and baseline scores associated with the endpoint. The proportion of responders, difference in responder rate, and 95% confidence interval for the responder rate based on Wald confidence limits will be presented based on the univariate summary. The odds ratio, and 95% confidence interval will be derived from the logistic regression model.

The analyses for confirmed disability improvement will be repeated for the RF and MMIA analysis sets as noted those respective sections.

9.4.2 **Disability Progression**

Disability progression on the EDSS + indicates clinically significant worsening on at least 1 of the components of the EDSS + (EDSS, T25FW, 9HPT [either hand]) as defined by the clinically significant change thresholds in Section 4.3.1). This will be based on the imputed dataset described in Section 9.3.1.

Progression on the EDSS + and each of its components will be analyzed by time point based on the criteria in Section 4.3.1. No confirmation will be required, i.e., progression at the analysis time point only is required.

The analysis will be presented at each time point with the number and percentage of subjects, and the 95% confidence interval for the proportion of subjects based on Wald

confidence limits, and the odds ratio and corresponding 95% confidence interval based on the logistic regression model including baseline as a covariate and treatment as a main effect.

9.4.3 **T25FW**

The change from baseline in the T25FW during the Treatment Period will be analyzed using an MMRM. In addition to the summaries noted in Section 9.1, the pooled standard deviation, effect size, and 95% confidence interval of the effect size will be noted.

9.4.4 9HPT

The change from baseline in the 9HPT-D and 9HPT-ND during the Treatment Period will be analyzed using an MMRM. In addition to the summaries noted in Section 9.1, the pooled standard deviation, effect size, and 95% confidence interval of the effect size will be noted.

9.4.5 **Exploratory Patient and Clinician Measured Scales**

The change from baseline in the total score for the MSIS-29, the total score for the BAC -Tower of London, the total score for the BAC - Verbal Memory, BAC - Tower of London T-score, BAC - Verbal Memory T-score, and the overall symptom score and most bothersome symptom score for the MSIOA will be analyzed at the collected time points using an MMRM.

